PROTOCOL TITLE: MICRO (Minimally Invasive Burch Colposuspension to Reduce Occult Stress

Incontinence)

Clinical trial registration: NCT03841513

PRINCIPAL INVESTIGATOR:

Name: [name]

Department: Obstetrics and Gynecology, Division of Female Pelvic Medicine and Reconstructive

Surgery

[contact] Email Address: [contact]

CO-INVESTIGATORS:

Name: [name]

Department: Obstetrics and Gynecology, Division of Female Pelvic Medicine and Reconstructive

Surgery

[contact]

Email Address: [contact]

Name: [name]

Department: Obstetrics and Gynecology, Division of Female Pelvic Medicine and Reconstructive

Surgery

[contact]

Email Address: [contact]

VERSION NUMBER: 5 **VERSION DATE: 10/6/20**

STUDY SUMMARY:

Investigational Agent(s)	N/A
(Drugs or Devices)	
IND / IDE / HDE #	
Indicate Special Population(s)	☐ Children ☐ Children who are wards of the state ☐ Adults Unable to Consent ☐ Cognitively Impaired Adults ☐ Neonates of Uncertain Viability ☐ Pregnant Women ☐ Prisoners (or other detained/paroled individuals) ☐ Students/Employees
Sample Size	50
Funding Source	Northwestern Friends of Prentice Grants Initiative
Indicate the type of consent to be obtained	

Version #: 2 Version Date: 10/6/20 Page 1 of 13

	Waiver of HIPAA Authorization			
	Waiver/Alteration of Consent Process			
Cit	Lead Site (For A Multiple Site Research Study)			
Site	☐ Data Coordinating Center (DCC)			
Research Related Radiation	Yes			
Exposure	⊠ No			
DSMB / DMC / IDMC	Yes			
	⊠No			

OBJECTIVES:

Purpose: The purpose of this study is to examine surgical outcomes when prophylactic minimally-invasive laparoscopic (including robotic) Burch colposuspension is performed at the time of laparoscopic sacrocolpopexy.

Hypothesis: Stress-continent women undergoing laparoscopic sacrocolpopexy will have higher rates of occult stress urinary incontinence without the addition of the laparoscopic Burch colposuspension.

Specific Goals and Objectives:

Primary Objective:

1. To determine if addition of laparoscopic Burch colposuspension to planned laparoscopic sacrocolpopexy improves rates of stress urinary incontinence (SUI) in stress-continent women undergoing sacrocolpopexy for pelvic organ prolapse (POP). SUI will be defined by a composite outcome of: positive retro-fill cough stress test at 300mL, answer of "yes" to question #17 of Pelvic Floor Distress Inventory 20 (PFDI-20), or any treatment for SUI.

Secondary Objectives:

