Sacrocolpopexy is the gold standard surgical repair of pelvic organ prolapse of the apical compartment. The Burch colposuspension is a retropubic procedure in which the periurethral tissue of the anterior vagina is affixed to Cooper's ligament on either side using permanent suture bridges. In the Colpopexy and Urinary Reduction Efforts (CARE) trial [2] patients without preoperative symptoms of SUI were randomized to receive or not to receive concomitant prophylactic Burch colposuspension at the time of abdominal sacrocolpopexy. At three months, the subjects who underwent the Burch procedure were found to have lower rates of SUI after surgery (33.6%) compared to the control group (57.4%). Furthermore, of patients who tested negative for SUI on preoperative urodynamic testing, 22.9 % of those who underwent the Burch procedure had SUI compared to 47.9% in the control group. Burch colposuspension did not increase the rate of urinary retention, urge incontinence, urinary urgency, urinary tract infection, intra or post-operative complications. The data in this trial supported the placement of prophylactic Burch colposuspension at the time of abdominal sacrocolpopexy.

Over the last decade, there has been a shift away from open routes of surgical access secondary to decreased morbidity and quicker recovery associated with minimally invasive procedures. [4-7] As a result, open abdominal sacrocolpopexy with Burch colposuspension has fallen out of favor, and minimally invasive laparoscopic sacrocolpopexy is performed with greater frequency. Additionally, midurethral slings (MUS) have become the gold standard surgical procedure for the treatment of SUI and are performed more frequently than Burch colposuspension at the time of prolapse surgery. The Outcomes Following Vaginal Prolapse Repair and Midurethral Sling (OPUS) study [3] examined the placement of prophylactic MUS at the time of vaginal prolapse surgery. Patients with MUS had lower rates of SUI than control group at 3 months (23.6% vs 49.4%) and at 12 months (27.3% vs 43%). However, unlike the CARE trial, patients with concomitant anti-incontinence procedure had higher rates of adverse events including bladder perforation (6.7% vs 0%), UTI (31.0% vs 18.3%), major bleeding (3.1% vs 0%), and incomplete bladder emptying at 6 weeks (3.7% vs 0%). In addition, MUS carries the risk of mesh erosion into the vagina or urinary tract.

Version #: 2 Version Date: 10/6/20 Page 3 of 13

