By studying the addition of laparoscopic (including robotic) Burch colposuspension to laparoscopic sacrocolpopexy, we anticipate optimizing surgical outcomes and minimizing complications for patients.

REFERENCES:

- 1. Wu, J.M., et al., Lifetime risk of stress urinary incontinence or pelvic organ prolapse surgery. Obstet Gynecol, 2014. 123(6): p. 1201-6.
- 2. Brubaker, L., et al., Abdominal sacrocolpopexy with Burch colposuspension to reduce urinary stress incontinence. N Engl J Med, 2006. **354**(15): p. 1557-66.
- 3. Wei, J.T., et al., A midurethral sling to reduce incontinence after vaginal prolapse repair. N Engl J Med, 2012. 366(25): p. 2358-67.
- 4. Geller, E.J., et al., Short-term outcomes of robotic sacrocolpopexy compared with abdominal sacrocolpopexy. Obstet Gynecol, 2008. 112(6): p. 1201-6.
- 5. Hsiao, K.C., et al., Comparison of laparoscopic and abdominal sacrocolpopexy for the treatment of vaginal vault prolapse. J Endourol, 2007. 21(8): p. 926-30.
- 6. Klauschie, J.L., et al., A comparison of laparoscopic and abdominal sacral colpopexy: objective outcome and perioperative differences. Int Urogynecol J Pelvic Floor Dysfunct, 2009. **20**(3): p. 273-9.
- 7. Paraiso, M.F., et al., Laparoscopic and abdominal sacral colpopexies: a comparative cohort study. Am J Obstet Gynecol, 2005. 192(5): p. 1752-8.

STUDY ENDPOINTS:

- 1. The primary study endpoint is to compare rates of SUI at 3 month post-operatively in patients who undergo laparoscopic sacrocolpopexy with and without Burch colposuspension. SUI will be defined by a composite outcome of: positive retro-fill cough stress test at 300mL, answer of "yes" to question #17 of Pelvic Floor Distress Inventory 20 (PFDI-20), or any treatment for SUI.
- 2. The secondary study endpoint is to compare complications, urinary symptoms, bowel symptoms, and sexual function in women with and without addition of laparoscopic Burch to sacrocolpopexy using the Pelvic Floor Distress Inventory 20 (PFDI-20) and Pelvic Organ Prolapse/Urinary Incontinence Sexual Questionnaire 12 (PISQ-12).

PROCEDURES INVOLVED:

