The primary outcome measure is stress incontinence symptoms 3-months after surgery. In CARE, 34% of women randomized to open Burch and 57% of controls had stress urinary incontinence 3-months after surgery. Assuming addition of a minimally invasive Burch colposuspension to minimally invasive sacrocolpopexy will result in similar rates of stress urinary incontinence, a sample size of 42 (21 in each group) would demonstrate that addition of a Burch is superior to no Burch with a superiority margin 15%, 80% power and type 1 error of 5%. Assuming a 15% study dropout rate, a total of 50 patients will be recruited for this study.

Data will be collected at Northwestern Medicine. All study data will be recorded on Data Collection Forms by a research coordinator or other member of the study team and securely maintained in a locked cabinet to which only study personnel have access. Data will be entered by a research coordinator at Northwestern into a REDCap database that will be stored on a secure server. Only study staff will have passwords to access the project data on REDCap. All users of REDCap need an institutional username and password to log in and to enter data. Research personnel, including study staff as well as study doctors, will be able to collect and have access to subject data.

Version #: 2 Version Date: 10/6/20 Page 9 of 13

After all data is collected, it will be downloaded from REDCap to Excel and SPSS and analyzed on Northwestern servers only and on computers that are Northwestern property and password protected by Northwestern.

PROVISIONS TO MONITOR THE DATA TO ENSURE THE SAFETY OF PARTICIPANTS

Adverse events associated with Burch colposuspension in conjunction with sacrocolpopexy will be recorded, and will include events such as post-operative urinary retention requiring catheterization, post-operative urinary tract infection, and persistent urinary urgency.

Subjects will be monitored at each study visit for adverse events. An assessment of adverse events form will be completed and will be recorded into REDCap electronic data capture system. The PI will be notified of any adverse events, which will be resolved with the patient.

PROVISIONS TO PROTECT THE PRIVACY INTERESTS OF PARTICIPANTS

To protect privacy interests, the personal health information collected for research purposes will be collected from the subject's electronic medical record to limit the amount of people they interact with and provide personal information to.

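### The 15% superiority margin in the sample-size paragraph fits neither the margin-free objective nor the stated 42 patients, and nothing in the plan says which null value decides the trial

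*Combined protocol and SAP*

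**What the plan says.** The combined protocol and SAP describes the primary comparison in four places.

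- OBJECTIVES, Hypothesis: stress-continent women "will have higher rates of occult stress urinary incontinence without the addition of the laparoscopic Burch colposuspension". No margin is given.
- OBJECTIVES, Primary Objective: "To determine if addition of laparoscopic Burch colposuspension to planned laparoscopic sacrocolpopexy improves rates of stress urinary incontinence (SUI"). No margin is given.
- STUDY ENDPOINTS, item 1: the aim is to "compare rates of SUI at 3 month post-operatively" with and without Burch, using the composite definition of SUI. No margin is given.
- DATA MANAGEMENT AND CONFIDENTIALITY, first paragraph: "a sample size of 42 (21 in each group") would show that "addition of a Burch is superior to no Burch with a superiority margin 15" per cent, with "80% power and type 1 error of 5" per cent. The planning rates come from the CARE trial: "34% of women randomized to open Burch and 57% of controls had stress urinary incontinence 3-months after surgery".

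The 15% appears only in that last paragraph. It is not said to be absolute or relative, and no sentence says the final result will be judged against it. There is no statistical analysis section. The only analysis details are that the data go to Excel and SPSS.

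**The concern.** A margin in a superiority statement moves the null value. The objective, read in the ordinary way, asks whether the SUI rate is lower with Burch, so the null is a difference of zero. The sample-size sentence, read literally, asks whether the benefit exceeds 15%. These have different thresholds, and the plan does not choose between them. Whoever analyses the trial could pick the null value after seeing the data, and the same result could be reported as positive or negative.

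The sample size brings in a third possibility. If 42 was calculated for yet another null, the number of patients, the wording and the objective all describe different trials.

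**Working it through.** Let D be the SUI rate without Burch minus the rate with Burch, so positive D is benefit.

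**Inputs.** From the sample-size paragraph: rates 0.57 and 0.34 (expected D = 0.23), 21 per group, margin 15% (taken as 0.15 absolute), 80% power, type 1 error 5% (sidedness not stated), dropout 15%. Allocation is equal (Randomization paragraph). Variance sum: v = 0.34×0.66 + 0.57×0.43 = 0.4695.

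**1. Reproducing 21 per group.** Unpooled formula: n = v(z_α + z_β)² / (distance from the null)². With z_β = 0.8416, (z_α + z_β)² is 6.183 one-sided and 7.849 two-sided.

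| Null for D | Distance | One-sided n | Two-sided n |
|---|---|---|---|
| +0.15 | 0.23 − 0.15 = 0.08 | 453.5, so 454 | 575.8, so 576 |
| −0.15 | 0.23 + 0.15 = 0.38 | 20.1, so **21** | 25.5, so 26 |

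For a null of zero, the usual pooled-null formula is n = [z_α√(2p̄q̄) + z_β√v]² / 0.23², with p̄ = 0.455, √(2p̄q̄) = 0.704 and √v = 0.685. It gives 57 one-sided and 73 two-sided.

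Of these, only the −0.15 null, one-sided at 5%, gives 21. Dropout then reproduces: 42/0.85 = 49.4, so 50. Reading 15% as relative does not rescue the figure: the distance becomes 0.85×0.57 − 0.34 = 0.1445, and n is 140 one-sided or 177 two-sided. The unrounded CARE rates in BACKGROUND ("were found to have lower rates of SUI after surgery (33.6%) compared to the control group (57.4"%) give 20 per group for the −0.15 form and 68 for two-sided superiority over zero, so the pattern is the same.

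**2. Observed difference needed at 21 per group.** Unpooled Wald limits with rates centred on 0.455; smallest D with D − z·SE above the null:

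- two-sided 5%: about 29 points against 0, about 42 against +15;
- one-sided 5%: about 25 points against 0, about 38 against +15.

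**3. Example results.**

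- 15/21 without Burch versus 7/21 with: D = 0.714 − 0.333 = 0.381, SE = √(0.00972 + 0.01058) = 0.1425. The 95% CI is 0.381 ± 0.279 = 0.102 to 0.660, and the one-sided 95% lower limit is 0.381 − 0.234 = 0.147. This is positive against 0 and negative against +15.
- 13/21 versus 5/21: D = 0.381, 95% CI 0.105 to 0.657, Fisher p = 0.028, one-sided lower limit 0.149. The conflict remains with an exact zero test.
- 10/21 versus 7/21: D = 0.143, 90% CI −0.104 to 0.389, Fisher p = 0.53. This clears −15 and shows no superiority.

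**4. How often the rules part.** Exact enumeration of two binomials, 21 per group, at 0.57 versus 0.34:

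- two-sided Wald: zero rule met 33.4%, zero met but +15 not met 21.4%;
- one-sided Wald: zero rule met 44.3%, zero met but +15 not met 30.3%;
- zero rule by two-sided Fisher's exact, +15 rule by two-sided Wald: disagreement about 8%.

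With 25 per group, that is with no dropout, these become 32%, 38% and 21%.

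With no true effect (0.57 in both arms, 21 per group), the one-sided −15 rule is met 23.6% of the time.

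**5. Power for the zero null at 21 per group.** Φ[(0.23√21 − z_α·0.704)/0.685], with 0.23√21 = 1.054. Two-sided: Φ(−0.476) = 32%. One-sided: Φ(−0.152) = 44%. Two-sided Fisher's exact, by enumeration: about 20%.

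**The case against.** The strongest reply is that the plan sets no success rule at all. The hypothesis, objective and endpoint are ordinary statements of intent, and a zero null is inferred from them. The 15% is one input in a sample-size sentence, beside power and type 1 error. This stands. A reader might infer that the plan declares two competing success criteria, any benefit and benefit above 15 points. The documents do not support that, because neither is written as a decision rule. But a sample-size statement does specify the hypothesis being powered, and with no rule anywhere else the choice of null stays open.

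A reader might also infer that the sponsor means to require a benefit above 15 points. The literal word superiority allows this, but the stated sample size speaks against it, since that rule needs 454 or more per group. Nor does the match with 21 prove that a non-inferiority trial was intended: it shows only which calculation yields the number.

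The disagreement rates depend on a test the plan does not name. Wald limits are liberal at 21 per group, and an exact zero test cuts 21% to about 8%. That also stands, so the size should be quoted as a range.

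Finally, a full correction of the sample-size sentence would have to state the null and so would settle this point. That is fair, but replacing the number or the power while leaving the margin wording in place would not.

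**Conclusion.** The point holds as an unresolved inconsistency. The wording, the objective and the sample size imply nulls of +15, 0 and −15 points, and the plan does not say which decides. Applying the margin in either direction gives an answer to a question the objective does not ask. At +15, an observed benefit of 38 points can fail. At −15, a trial of a procedure with no effect passes about 24% of the time; that would be a legitimate statement that Burch is not worse by 15 points, but a false one if reported as superiority.

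The zero and +15 rules disagree in about 8% to 30% of trials at the planning rates with 21 per group, depending on test and sidedness. These figures assume that 15% is absolute (the reading under which 21 is reproduced), that the CARE rates apply, and that 21 per group are analysed.

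**What to change.** In STUDY ENDPOINTS item 1 and in the sample-size paragraph, before the data are analysed:

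1. State that the primary test is of no difference in the 3-month composite SUI rate between the randomised groups. Name the test and its sidedness, and report the risk difference with its 95% CI.
2. Delete the 15% margin as a criterion. If 15 points is meant as a clinically important difference, say that it is absolute and used only to interpret the interval.
3. Deleting the margin leaves 42 without a derivation. Replace the 80% with the power at 21 per group for the test chosen: about 32% two-sided or 44% one-sided by normal approximation, or about 20% with two-sided Fisher's exact.

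The cost is a few sentences of amended text, with no effect on enrolment or conduct. The restated power will show that a non-significant result cannot be read as evidence of no benefit. Whether to enlarge the trial is a separate decision: 80% power against zero would need 57 (one-sided) to 73 (two-sided) per group before dropout.

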Participants may inquire about the individual measurements of their exam if desired. Patients can be unblinded after their 3 month visit. Study results may be given to patient at the completion of the study.

STUDY TIMELINES

An individual will participate in the study for a maximum of 4 months from the time of enrollment. Participants will be enrolled in the study at their preoperative visit and will be evaluated again in the postoperative recovery room, at the 2 week and 3 month post-operative visits.

We originally anticipated that it would take 24 months to enroll 50 patients however recruitment has taken longer. Adding an additional recruitment site will help us with our efforts. We anticipate recruitment will be completed December 2021 with analysis completed by June 2022.

	Months 1-12	Months 4-15	Months 15-16
Patient Enrollment	Χ		
Patient Follow-up		Х	
Period			
Data Analysis			Х

INCLUSION AND EXCLUSION CRITERIA

Inclusion Criteria

- Women over age 18
- English or Spanish speaking and reading
- Symptomatic pelvic organ prolapse with any compartment at or beyond the hymen

- Stress-continent, as defined as response of "no" to question 17 of PFDI-20: "Do you usually experience urine leakage related to coughing, sneezing, or laughing?", as well as a negative empty supine stress test.
- Planning laparoscopic or robotic sacrocolpopexy, with or without hysterectomy
- Have completed childbearing

Exclusion Criteria

- Adults unable to consent
- Pregnant women or patients desiring future pregnancy
- Patients undergoing uterine sparing surgery
- Individuals under age 18
- Prior procedure for stress urinary incontinence
- Prior retropubic surgery

VULNERABLE POPULATIONS

N/A

RECRUITMENT METHODS

This study will recruit patients who present to the Urogynecology Clinic at the Integrated Pelvic Health Program (IPHP), Lake Forest Hospital, and Central DuPage Hospital, at the time of their initial or follow up surgical consult appointment. Specifically, women without symptoms of SUI, defined as a negative answer in response to question #17 in the Pelvic Floor Distress Inventory (PFDI)-20 who are planning to undergo minimally invasive sacrocolpopexy for symptomatic POP at or beyond the hymen will be approached for recruitment. There will be no external advertising.

COMPENSATION FOR PARTICIPATION IN RESEARCH ACTIVITIES

Study participants will receive a \$100 gift card at the end of the study follow up period.

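### On the protocol's own rates (34% vs 57%), 21 per group gives about 31–34% power (two-sided) or 43–46% (one-sided) for plain superiority, not the stated 80%

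*Combined protocol and SAP*

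**What the plan says.** The sample-size justification is in the combined protocol and SAP, at the start of Data Management and Confidentiality. It takes its rates from the CARE trial, where "34% of women randomized to open Burch and 57% of controls had stress urinary incontinence 3-months after surgery", and assumes similar rates here. It then states that "a sample size of 42 (21 in each group") would show that Burch "is superior to no Burch with a superiority margin 15%, 80% power and type 1 error of 5" per cent. Allowing for 15% dropout, this becomes 50. The paragraph names no formula, test or sidedness.

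The rest of the protocol describes an ordinary superiority question. The hypothesis under Objectives is that stress-continent women "will have higher rates of occult stress urinary incontinence without the addition of the laparoscopic Burch colposuspension". Under Study Endpoints, "The primary study endpoint is to compare rates of SUI at 3 month post-operatively". Neither mentions a margin, and non-inferiority appears nowhere.

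**The concern.** A 23-point difference between two proportions near one half normally needs far more than 21 per group for 80% power. A superiority margin should raise the requirement further, because only the part of the effect beyond the margin counts. The stated size looks too small on either reading.

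This is the only justification of the sample size, and it concerns the primary endpoint. If the 23-point benefit is real, a two-sided chi-square test on 42 patients would miss it about two times in three, and a one-sided test slightly more than half the time. A reader who trusts the 80% could take a non-significant result as evidence that Burch does not help.

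**Working it through.** **Inputs.** Sample-size paragraph: p₁ = 0.34 (Burch), p₂ = 0.57 (control), difference d = 0.23, margin 0.15, 21 per group, type 1 error 5%, power 80%, dropout 15%. Allocation is 1:1 (Randomization). Sidedness is not given, so both cases are shown.

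V = 0.34 × 0.66 + 0.57 × 0.43 = 0.2244 + 0.2451 = 0.4695.

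**1. Reproducing the plan's figure.** Unpooled formula: n per group = (z_α + z_β)² V / Δ², with (1.645 + 0.842)² = 6.183 one-sided and (1.960 + 0.842)² = 7.849 two-sided.

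| Distance to the null, Δ | One-sided 5% | Two-sided 5% |
|---|---|---|
| 0.23 (plain superiority) | 54.9 → 55 | 69.7 → 70 |
| 0.23 − 0.15 = 0.08 (superior by more than 15 points) | 453.5 → 454 | 575.8 → 576 |
| 0.23 + 0.15 = 0.38 (margin added to effect) | 20.1 → **21** | 25.5 → 26 |

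With pooled variance under the null, plain superiority needs 56.9 → 57 (one-sided) or 72.4 → 73 (two-sided).

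On the stated rates, only the margin-added, one-sided row gives 21. That is a non-inferiority calculation: it would show only that Burch is not more than 15 points worse. The dropout step does reproduce: 42 / 0.85 = 49.4 → 50.

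**2. Power at the planned size, zero margin.** The unpooled power is Φ(d / √(V/n) − z_α). At n = 21, √(0.4695/21) = 0.1495 and 0.23/0.1495 = 1.538. So the power is Φ(1.538 − 1.960) = 33.7% two-sided and Φ(1.538 − 1.645) = 45.8% one-sided.

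| Method | 21/group, two-sided | 21/group, one-sided | 25/group, two-sided | 25/group, one-sided |
|---|---|---|---|---|
| Normal, unpooled | 33.7% | 45.8% | 38.9% | 51.3% |
| Normal, pooled | 31.7% | 43.9% | 36.8% | 49.5% |
| Chi-square, exact enumeration | 31.2% | 42.7% | 41.8% | 53.4% |
| Fisher's exact | 20.3% | 30.3% | 30.8% | 41.8% |

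The 25-per-group columns assume that all 50 patients are evaluable.

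**3. Power with the margin read literally.** At 21 per group, one-sided 5%: Φ(0.08/0.1495 − 1.645) = 13.4%; exact enumeration of the Wald test gives 14.0%.

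**4. Other CARE rates in Background.** At 21 per group, the unrounded 33.6% vs 57.4% gives 33–36% two-sided or 45–48% one-sided. In the urodynamic-negative subgroup, "22.9 % of those who underwent the Burch procedure had SUI compared to 47.9% in the control group"; those rates give 39–42% or 52–54%. Neither approaches 80%.

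**5. What 42 evaluable patients can do.** From a control rate of 57%, the difference with 80% power is:
- two-sided: 38.5 points (unpooled), 39.9 (exact chi-square) or 40.5 (pooled);
- one-sided: 35.0, 36.6 or 36.5 points.

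The expected 95% CI half-width is 1.96 × 0.1495 = 29.3 points. An observed 23-point benefit would run from about −6 to +52 points.

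**The case against.** Four points can be made for the plan or against this criticism.

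- **No test is named, so the replacement power is not a single number.** This stands. The 31–34% and 43–46% apply to chi-square or normal tests. Fisher's exact test, a common choice at this size, gives 20% and 30%. At 25 per group the exact chi-square values of 42% and 53% are flattering, because the test's true size there is about 6.0–6.5% two-sided and 5.6–5.9% one-sided at common rates of 0.40–0.55. All of this moves further from 80%.
- **The non-inferiority origin is a guess.** It is. The paragraph shows no formula, and the urodynamic-negative rates with the margin added also round to 21 at two-sided 5% (7.849 × 0.4261 / 0.40² = 20.9). No proposed analysis adds the margin to the effect. The shortfall in step 2 needs no explanation of where 21 came from.
- **The zero-margin reading sets aside the stated margin.** It follows the hypothesis and endpoint, and it is the more generous superiority reading; the literal margin leaves 13–14%.
- **The study is small and recruitment is slow.** Study Timelines says: "We originally anticipated that it would take 24 months to enroll 50 patients however recruitment has taken longer". That is a reason not to enlarge the trial, but not a reason to keep an incorrect power statement.

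**Conclusion.** The power statement is wrong as written, and it must be corrected. With 34% vs 57% and 42 evaluable patients, power for superiority is 31–34% two-sided or 43–46% one-sided, against 80% stated. Even if all 50 are evaluable and the test is one-sided, it is about a coin flip at best.

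This rests on the protocol's own rates, equal allocation, a 5% level and a chi-square or normal test of no difference. No sidedness, superiority margin or alternative CARE rate examined restores 80%. Rounding or choice of formula cannot explain the gap: plain superiority needs 55 to 73 per group, or 2.6 to 3.5 times 21. Confidence is high on the shortfall. The source of the error remains an inference.

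**What to change.** Keep 50 patients and rewrite the sample-size paragraph:

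1. State the primary null hypothesis as a risk difference of zero on the composite SUI endpoint defined under Objectives and Study Endpoints. The sample-size paragraph itself refers only to symptoms and should be aligned with that definition.
2. Name the test and its sidedness.
3. Remove the 15% margin, or state its role. It must not be added to the effect in the analysis. As an illustration only, since nobody has proposed it: a one-sided Wald test with the margin added, at 21 per group, would declare success 27%, 23% or 24% of the time when both true rates are 0.34, 0.45 or 0.57.
4. Replace the 80% with the power of the chosen test at 42 evaluable: 31–34% two-sided or 43–46% one-sided for chi-square, about 20% or 30% for Fisher. Add the difference that does have 80% power: about 39–40 points two-sided or 35–37 one-sided for chi-square. Fisher needs a larger difference; at 40 points it has 68% two-sided.
5. Commit to reporting the risk difference with its 95% CI, and say that a non-significant result is not evidence of no benefit.

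The cost is protocol wording and a much less favourable power figure. It should be settled before the results are analysed.

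Keeping 80% power would instead need these totals after 15% dropout, with equal groups and an uncorrected test:
- one-sided: 110/0.85 → 130 to 114/0.85 → 136;
- two-sided: 140/0.85 → 166 to 146/0.85 → 172.

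That is about 2.6 to 3.4 times 50, and more still under Fisher (77% power at 73 per group two-sided, 76% at 57 one-sided). Given the recruitment record, this may not be practical.
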